Official Title: Safety and feasibility of Early Oral Nutrition after Endoscopic Treatment for Patients with Liver Cirrhosis: A Historical-prospective, Comparative Effectiveness study

NCT number: NCT04823780

Document date: September 1, 2020

Study protocol

The purpose of the study was to compare safety and effectiveness of different feeding time in the real-world clinical practice. Detailed history-taking and physical examination were carried out on all recruited patients and basic information were recorded including liver function by Child-Pugh's scores and MELD scores, endoscopic features. EVL was performed after confirmation of esophageal varices and cyanoacrylate was injected if gastric varices were diagnosed. Further, the octreotide was given for 24 hours postop routinely. All the therapeutic endoscopies were performed by a technically proficient gastrointestinal endoscopist. The endoscopist, data collectors and statisticians were blinded to the follow-up dietary intervention tasks.

Eligible patients in the EN group were required to fast for 4 hours following endoscopic treatment and peptisorb produced by Milupa Nutricia GmbH was used for enteral nutrition at the beginning. The initial recommended dose of peptisorb is 60 g dissolved in 250ml water, which can provide 250 kcal energy (protein 9.8 g, fat 2.45 g, carbohydrate 46.5 g). Transition to soft diet such as chicken custard could be carried out after 2 to 3 times of giving peptisorb emulsion if there were no adverse reactions. Further, it is recommended that the diet of patients should obey the principle of multiple-meal-with-small-amount-for-each and the daily meals could up to between 4 and 5 times. The time and amount of diet was recorded specifically and the total energy intake through enteral nutrition were calculated. Extra energies were supplemented by parenteral nutrition. All patients required fasting for at least 48 hours in the control group and parenteral nutrition was provided through intravenous infusion, then transit gradually from liquid diet to soft diet. All nutritional supports were provided based on the standard recommended by ESPEN guideline on clinical nutrition in liver disease that calorie requirement for $30 \sim 35 \text{ kcal} \cdot \text{kg}^{-1} \cdot \text{d}^{-1}$.

In addition, the prospectively enrolled patients in interventional group were divided into three subgroups according to dietary time. The early enteral nutrition (EEN) in the current study was defined as starting enteral nutrition between 4 and 12 hours after endoscopic therapy and delayed enteral nutrition (DEN) was defined as between 12 and 48 hours. The dietary time after 48 hours was defined as parenteral nutrition (PN).

Outcomes and definitions

The primary endpoint of this study was variceal re-bleeding following endoscopic treatment. The secondary endpoints were mortality whereas the adverse events during the 42-day follow-up. The days and expenses of hospitalization were also compared between the two groups in this study. Besides, inflammatory factor, serum albumin level, defecation time and the satisfaction with nutritional support of patients were also evaluated in the three subgroups.

Variceal Re-bleeding includes very early rebleeding and early rebleeding. In this study, very early rebleeding was defined as rebleeding within 5 days after endoscopic treatment whereas early rebleeding was defined as within 5 and 42 days after endoscopic treatment. Rebleeding within 48 hours was considered as failure treatment. Whatever anytime, once the rebleeding occurred, the patients would receive pharmacotherapy or endoscopic treatment again.

Satisfaction of the patients with nutritional support was assessed based on 5 - point Likert scale of very satisfied (5 points), satisfied (4 points), neither satisfied nor dissatisfied (3 points), dissatisfied (2 points) and very dissatisfied (1 point). The satisfaction rate was regarded as the proportion of very satisfied and satisfied.

Statistical analysis

Statistical analyses were performed using statistical software IBM SPSS Statistical 26.0 (SPSS, Chicago, IL). The baseline data of control group and intervention group were matched using propensity score analysis (PSM) in a ratio fashion of 1:1 using the nearest neighbor technique. Quantitative variables conforming to normal distribution were expressed as mean \pm standard deviation ($M \pm SD$) whereas the variables not conforming to normal distribution were presented as median (interquartile range (IQR), (P25, P75)). Qualitative variables were expressed as percentages. Quantitative variables were compared using Student's *t*-test, Mann-Whitney nonparametric test or variance analysis, and χ^2 test. On the other hand the Fisher's exact tests were used to compare qualitative variables in this study. Linear regression analysis was performed to find the significant factors influencing diet time after endoscopic treatment. The analysis of outcomes between the two groups was conducted based on intention-to-treat

(ITT) and per-protocol (PP) analysis. $P < 0.05$ was considered statistically significant.

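### The EEN, DEN and PN subgroups are formed by when feeding actually started, and no adjusted comparison of their outcomes is planned, so baseline differences can pass as feeding effects

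*Combined protocol and SAP*

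**What the plan says.** The Study protocol section ends by stating that "the prospectively enrolled patients in interventional group were divided into three subgroups according to dietary time". Early enteral nutrition (EEN) means a start at 4–12 h after endoscopy, delayed enteral nutrition (DEN) 12–48 h, and parenteral nutrition (PN) after 48 h. No randomisation, schedule, clinical criterion or patient choice is given as the reason a patient falls in one window rather than another.

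Outcomes and definitions then states that "inflammatory factor, serum albumin level, defecation time and the satisfaction with nutritional support of patients were also evaluated in the three subgroups". It also says "Rebleeding within 48 hours was considered as failure treatment", without saying which subgroup holds a patient who rebleeds or dies before being fed.

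Statistical analysis deals with baseline imbalance once: "The baseline data of control group and intervention group were matched using propensity score analysis". It limits the analysis sets in the same way: "The analysis of outcomes between the two groups was conducted based on intention-to-treat" and per-protocol. The tests for quantitative variables are Student's t-test and "Mann-Whitney nonparametric test or variance analysis", with chi-square and Fisher's exact tests also listed. None has covariates. The only regression is this: "Linear regression analysis was performed to find the significant factors influencing diet time after endoscopic treatment".

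**The concern.** A subgroup defined by when feeding happened is an observed exposure, not an assigned one. If patients with worse liver disease or a harder endoscopy are fed later, EEN, DEN and PN differ before any feeding takes place. Balance between control and intervention does not create balance among three subsets of the intervention group. The regression on diet time shows that the plan itself allows for other factors influencing feeding time, yet those factors are not carried into any outcome comparison.

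The stated purpose is to compare different feeding times, and only this comparison separates 4–12 h from 12–48 h. A P value below 0.05 here could reflect who was fed late rather than what late feeding does.

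Two definitional gaps add to this:

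- A bleed or death before the first meal can itself determine the recorded feeding time.
- The Study protocol section gives the EN group a 4-hour fast and the control group at least 48 hours, yet a subgroup fed after 48 h sits inside the intervention group. The 4 hours may be meant as a minimum, but the text does not say so. As written, PN patients share the control group's feeding window, which may also bear on the two-group contrast.

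**Working it through.** **Reading the text.** The plan states no sample size, effect size or subgroup count, so there is no figure to reproduce. Each place where adjustment might be found was checked:

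| Element of the plan | Scope | Adjusts subgroup outcomes? |
|---|---|---|
| 1:1 propensity matching | Control vs intervention | No |
| ITT and PP | The two groups | No |
| t-test, Mann-Whitney, analysis of variance, chi-square, Fisher | General list | No covariates named |
| Linear regression | Diet time as dependent variable | Models exposure, not outcome |
| 4-hour fast | EN group | Does not say who falls in which window |

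**Illustration: every input is assumed.** There are 120 patients, EEN/DEN/PN = 72/36/12, and no feeding effect. Albumin has within-group SD 5 g/L. Baseline means are g, g/2 and 0. Follow-up = r × baseline + shift (u, u/2, 0) + noise, again with within-group SD 5. The shift u stands for an unrecorded factor or a post-endoscopy event.

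*Unadjusted.* The spurious EEN–PN difference is d = r·g + u. Subgroup means are d, d/2 and 0, with weighted mean (72d + 18d)/120 = 0.75d. The noncentrality is

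λ = [72(0.25d)² + 36(0.25d)² + 12(0.75d)²]/25 = 13.5d²/25 = 0.54d².

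For g = 3, r = 0.7, u = 0: d = 2.1 g/L and λ = 2.38. Noncentral F on 2 and 117 df gives P<0.05 in 25.6% of studies. For r = 0.5: d = 1.5 g/L, λ = 1.215, 14.9%.

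| g (g/L), u = 0 | r = 0.7 | r = 0.5 |
|---|---|---|
| 2 | 13.6% | 9.2% |
| 3 | 25.6% | 14.9% |
| 4 | 42.7% | 23.6% |

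*ANCOVA on baseline, g = 3* (20,000 simulated studies per cell):

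| u (g/L) | r | Unadjusted: difference, P<0.05 | ANCOVA: difference, P<0.05 |
|---|---|---|---|
| 0 | 0.7 | 2.1 g/L, 25.6% | 0.0 g/L, 5.1% |
| 0 | 0.5 | 1.5 g/L, 14.9% | 0.0 g/L, 5.0% |
| 1 | 0.7 | 3.1 g/L, 50.9% | 1.0 g/L, 13.1% |
| 1 | 0.5 | 2.5 g/L, 34.9% | 1.0 g/L, 10.5% |
| 2 | 0.7 | 4.1 g/L, 76.3% | 2.0 g/L, 40.9% |
| 2 | 0.5 | 3.5 g/L, 61.7% | 2.0 g/L, 28.9% |

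A noncentral-F check of the ANCOVA figures for u = 1 and 2 gives 13.2% and 41.2% (r = 0.7), and 10.4% and 29.2% (r = 0.5). The clean result at u = 0 holds by construction.

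*Continuous outcome without a baseline value.* Suppose a recorded severity score differs by 0.6 SD (EEN–PN) and correlates ρ with the outcome. The spurious difference is 0.6ρ and λ = 13.5(0.6ρ)². For ρ = 0.3 this is 0.18 SD, with P<0.05 in 8.4%. For ρ = 0.5 it is 0.30 SD and 14.9%.

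**Precision (95% half-widths, EEN–PN).**

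- Albumin unadjusted: 1.96 × 5 × √(1/72 + 1/12) = 3.06 g/L.
- Albumin ANCOVA: 1.96 × 5 × √(1 − r²) × √(1/72 + 1/12 + 9/(117 × 25)) = 2.22 g/L (r = 0.7) or 2.69 g/L (r = 0.5).
- No-baseline outcome unadjusted: 1.96 × √(1/72 + 1/12) = 0.611 SD.
- No-baseline outcome adjusted: 1.96 × √(1 − ρ²) × √(1/72 + 1/12 + 0.36/117) = 0.621, 0.592 or 0.538 SD for ρ = 0, 0.3 or 0.5.

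**The case against.** The affected outcomes come last in the list, after the primary and secondary endpoints and the comparison of hospital stay and cost. Rebleeding and mortality are not assigned to the subgroups, and no causal subgroup hypothesis is stated. That stands, and it limits the severity.

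The general test list is not tied to this comparison. However, analysis of variance is its natural reading for quantitative outcomes in three groups, and chi-square or Fisher fits the satisfaction rate. That is fair: the fault is the absence of covariates rather than of any usable test.

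The illustration is not evidence about this trial, and it moves with its inputs. At r = 0.7, a 1 g/L gap gives 7%. With the 3 g/L gap, a 100/16/4 split gives 15% and an equal split 36%. The larger percentages depend on an assumed unrecorded shift, and adjustment does not remove that part. All of this stands, so the numbers show a mechanism and not an estimate.

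Baseline albumin is not explicitly listed as recorded, so ANCOVA can be used only where a value was measured. Adjusting a binary satisfaction rate for several covariates could be unstable if PN is very small. Both points limit the fix but do not defend an unadjusted comparison, because the plan applies P<0.05 without distinction and never calls these results descriptive.

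**Conclusion.** The concern holds. The plan forms EEN, DEN and PN by observed feeding time, gives no assignment rule, and specifies no adjusted analysis of their outcomes. Followed as written, it gives comparisons open to confounding. That conclusion rests on the text alone.

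Size and direction cannot be derived from the documents. Under the assumed 72/36/12 split with no unrecorded shift, baseline albumin gaps of 2–4 g/L raise the false-positive rate from 5% to between 9% and 43%. Adjustment reduces the error but does not remove it where unrecorded factors or early events also differ. Because the outcomes are supplementary, this is something to fix rather than a threat to the primary analysis.

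**What to change.** In Statistical analysis, specify that the three subgroups are compared by regression adjusted for a short, prespecified list drawn from the data already collected, since "basic information were recorded including liver function by Child-Pugh's scores and MELD scores, endoscopic features". For albumin and inflammatory factor, use ANCOVA on the baseline value where one was measured, with a rule for missing baselines. Label the results observational and exploratory, because unrecorded confounding and feeding delayed by post-endoscopy events remain. Where a subgroup is too small to support adjustment, present that comparison as descriptive, without a test.

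In the Study protocol and Outcomes sections:

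- State how feeding time was set.
- State how patients who rebleed or die before first feeding are placed, consistently with the 48-hour treatment-failure rule.
- Reconcile the EN group's 4-hour fast with a PN subgroup fed after 48 h inside the intervention group.

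The cost is SAP wording and a little more analysis. In the illustration, ANCOVA narrows the albumin interval. For a continuous outcome without a baseline value, the half-width falls from 0.611 to 0.592 SD if severity correlates 0.3 with the outcome, and widens slightly to 0.621 SD if it does not correlate. Neither baseline albumin nor a baseline inflammatory factor is explicitly listed as recorded, so their availability needs checking first.

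### EEN, DEN and PN appear to be formed by the feeding time reached, are compared without baseline adjustment, and have no rule for patients who rebleed or die before the first feed

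*Combined protocol and SAP*

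**What the plan says.** The last paragraph of the Study protocol section says that "the prospectively enrolled patients in interventional group were divided into three subgroups according to dietary time". EEN starts at 4 to 12 hours after endoscopy, DEN at 12 to 48 hours, and PN after 48 hours. The same section gives the EN group a 4-hour fast and says that the time and amount of diet were recorded. It also lists Child-Pugh, MELD and endoscopic features as baseline data.

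Under Outcomes and definitions, rebleeding is timed from the same endoscopy. "Rebleeding within 48 hours was considered as failure treatment", and "once the rebleeding occurred, the patients would receive pharmacotherapy or endoscopic treatment again". The outcomes named for the subgroups are these: "inflammatory factor, serum albumin level, defecation time and the satisfaction with nutritional support of patients were also evaluated in the three subgroups".

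Under Statistical analysis, propensity matching is described for control versus intervention only. "Linear regression analysis was performed to find the significant factors influencing diet time after endoscopic treatment". ITT and PP analyses are named for the comparison of the two groups, and PP is not defined.

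**The concern.** Feeding time is recorded after endoscopy and is itself modelled as something that other factors influence. It therefore reads as an observed variable and not as an assignment, although the documents do not say so outright. Two problems follow.

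First, sicker patients may be fed later. The subgroup comparisons carry no baseline adjustment, so a difference between EEN and PN can reflect prognosis.

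Second, rebleeds and deaths can fall inside the 48 hours that decide subgroup membership. Calling a rebleed within 48 hours a treatment failure labels the outcome. It does not say where the patient is counted. A patient who dies unfed has no feeding time at all, so some rule is unavoidable. The same gap affects PP: if late-fed intervention patients are excluded, early events can be removed from the intervention group only. The stated purpose is to compare the safety and effectiveness of different feeding times, so this bears on what the study can conclude.

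**Working it through.** The documents give no sample size, rebleeding rate or feeding-time distribution, so there is no figure to reproduce. Every input below is an assumption, with no true effect of feeding unless stated.

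**Inputs.** Rebleeding by day 42 is 15%. A quarter of it, 3.75%, is spread evenly over 0–48 h, and the other 11.25% evenly over the remaining 960 h (42 × 24 − 48). Planned first feed is EEN 50%, DEN 35%, PN 15%, uniform within 4–12, 12–48 and 48–72 h (means 8, 30 and 60 h).

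**Step 1: rebleeds before the planned feed.**
- EEN: 3.75 × 8/48 = 0.625%
- DEN: 3.75 × 30/48 = 2.344%
- PN: 3.75 + 11.25 × 12/960 = 3.891%
- Whole intervention group: 0.50 × 0.625 + 0.35 × 2.344 + 0.15 × 3.891 = 1.72%

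**Step 2: 42-day rebleeding by handling rule.**

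| Rule for pre-feed rebleeds | EEN | DEN | PN | EEN/PN |
|---|---|---|---|---|
| Kept in planned subgroup (no delay in feeding) | 15.0% | 15.0% | 15.0% | 1.00 |
| Feeding delayed 24 h | 14.5% | 15.2% | 16.2% | 0.90 |
| Placed in PN (as with a 48 h delay) | 14.5% | 13.0% | 21.0% | 0.69 |
| Dropped | 14.5% | 13.0% | 11.6% | 1.25 |

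- EEN in the last two rows: (15 − 0.625)/(100 − 0.625) = 14.5%. DEN: (15 − 2.344)/(100 − 2.344) = 13.0%.
- PN with the others added, as a share of the whole group: (0.15 × 15 + 0.50 × 0.625 + 0.35 × 2.344)/(15 + 0.3125 + 0.820) = 3.383/16.133 = 21.0%.
- PN with its own dropped: (15 − 3.891)/(100 − 3.891) = 11.6%.
- The 24 h row comes from numerical integration of the same model.

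A separate simulation used a 40/35/25 split, 5–20% rebleeding and 10–40% of events within 48 h. EEN/PN was 0.66–0.90 with placement in PN and 1.09–1.56 with dropping.

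**Step 3: listed outcomes.** With placement in PN, the share that rebled within 48 h is 10.5% in PN ((0.15 × 3.75 + 0.3125 + 0.820)/16.133) and 3.1% in EEN (3.125/99.375), a gap of 7.4 points. If a rebleed lowers albumin by 3–5 g/L (assumed), PN is lower by 0.22–0.37 g/L. If it lowers the satisfaction rate by 30–50 points (assumed), PN is lower by 2.2–3.7 points. With dropping, the gap is 3.1 points the other way: 0.09–0.16 g/L and 0.9–1.6 points. No figure is available for inflammatory factor or defecation time.

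**Step 4: prognosis.** Suppose 40% of patients are high risk (25% rebleeding; 8.3% in the rest) and their planned split is 30/45/25, with 50/35/15 overall. The high-risk share is 0.4 × 0.30/0.50 = 24% in EEN and 0.4 × 0.25/0.15 = 67% in PN. With no feeding effect, rebleeding is 0.24 × 25 + 0.76 × 8.3 = 12.3% in EEN and 0.667 × 25 + 0.333 × 8.3 = 19.4% in PN. Restricting to patients free of rebleeding at 48 h does not remove this: 9.5/13.2/15.3% unadjusted, against 11.7% in all three after adjustment.

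**Step 5: PP, control at 15%.**
- PP means fed by 48 h, all pre-feed bleeders excluded: (0.50 × 14.375 + 0.35 × 12.656)/(0.50 × 99.375 + 0.35 × 97.656) = 13.85%, RR 0.92. With no feeding delay the RR is 1.00.
- PP means fed at 4–12 h: 14.5/15, RR 0.96.
- A late feed after a rebleed is excused, but event-free late-fed patients are still excluded: (12.75 + 0.5625)/(85 + 0.5625) = 15.6%, RR 1.04 for the 48 h definition. For 4–12 h, bleeders before 12 h are excused (3.75 × 12/48 = 0.9375%): (7.5 + 0.469)/(50 + 0.469) = 15.8%, RR 1.05.

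**Step 6: what a 48 h landmark hides.** With no effect it gives 11.25/96.25 = 11.7% in every subgroup. Now let feeding double the risk until 48 h. In EEN, fed on average at 8 h, early events become 3.75 × (8 + 2 × 40)/48 = 6.9%. The 42-day risk is 6.875 + 93.125 × 0.1169 = 17.8% against 15%, RR 1.18. The landmark RR is still 1.00.

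**The case against.** The strongest reply is about reach. The large gaps in Step 2 concern rebleeding by subgroup, and the plan does not list that analysis. For albumin and satisfaction the shifts are small even in the extreme case. The two-group ITT comparison is untouched, since the intervention group keeps its late-fed patients. Nothing in the documents says that a rebleed postpones feeding. The blinding sentence treats diet as an intervention task, which could suggest assigned timing. All of this stands and limits the point. It does not supply the missing rule or the missing adjustment, and the planned regression on diet time favours the observed reading.

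Two stronger readings are tempting, and the documents support neither.
- A reader might infer that the grouping makes late feeding look harmful. The direction depends on an unstated rule: dropping pre-feed bleeders reverses it, and keeping them with no feeding delay leaves no bias.
- A reader might infer that a 48-hour landmark is simply the better comparison. It resolves classification, but it discards the events that the plan itself calls treatment failure. These belong to the primary endpoint and fall when harm from early feeding could appear (Step 6). It also needs baseline adjustment (Step 4).

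**Conclusion.** The point holds in limited form and should be fixed; confidence is medium. The text shows no baseline adjustment for the subgroup comparisons and no subgroup or PP status for a patient with an event before the first feed. That dietary time means the time reached is the best reading, not an explicit statement.

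The possible bias runs in either direction. In the base case the null EEN/PN ratio for rebleeding ranges from 0.69 to 1.25 according to the rule chosen, and PP relative risks run from 0.92 to 1.05 according to the definition. These figures rest wholly on assumed rates and feeding times, and pre-feed deaths were not modelled. For albumin and satisfaction the shift is at most about 0.4 g/L and 4 points under the assumed decrements.

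**What to change.** 1. Adjust the EEN/DEN/PN comparisons for a few prespecified baseline factors already recorded (Child-Pugh, MELD, endoscopic features), and describe them as observational. State what dietary time means and where patients with a pre-feed event are counted.
2. Keep ITT as the reference for the two-group comparison. Define PP, and do not count late or absent feeding that follows a rebleed or death as a deviation, so that early events are not removed from the intervention group only. If event-free late-fed patients are still excluded, a small bias the other way remains (RR 1.04–1.05 in Step 5), so PP should be read beside ITT. Weighted censoring could address this but is more than re-coding.
3. Report all rebleeds and deaths from endoscopy to 48 hours for all patients, marking those before the first feed. Use a 48-hour landmark only as a secondary analysis. If rebleeding, death or adverse events are analysed by feeding time, count from endoscopy with feeding as a time-varying exposure and baseline adjustment. This requires event times finer than the bands in Outcomes and definitions, and the documents do not say that they were collected.
4. Reconcile the 4-hour fast for the EN group with the intervention subgroup first fed after 48 hours, so that adherence can be determined.

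The cost is some wording, a little more analysis, and a few degrees of freedom in subgroups that may be small. No sample size is given, so the covariate list should stay short.

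### Feeding time is recorded individually, but the prospective comparisons use it only as three unordered, unadjusted bands; an adjusted analysis on hours to first feed should be added beside them.

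*Combined protocol and SAP*

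**What the plan says.** The Study protocol section gives the purpose as comparing feeding times in routine practice. For the enteral nutrition group it states that "The time and amount of diet was recorded specifically". At the end of that section, "the prospectively enrolled patients in interventional group were divided into three subgroups according to dietary time". Early enteral nutrition (EEN) is "starting enteral nutrition between 4 and 12 hours after endoscopic therapy"; for the next band, "delayed enteral nutrition (DEN) was defined as between 12 and 48 hours"; a first feed after 48 h is labelled parenteral nutrition (PN).

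Outcomes and definitions assigns four outcomes to these bands: "inflammatory factor, serum albumin level, defecation time and the satisfaction with nutritional support of patients were also evaluated in the three subgroups". Rebleeding, mortality, adverse events, hospital days and cost are not assigned to them.

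For quantitative outcomes, Statistical analysis lists Student's t-test and "Mann-Whitney nonparametric test or variance analysis". One model uses diet time as a number, but with diet time as the outcome: "Linear regression analysis was performed to find the significant factors influencing diet time after endoscopic treatment". No trend test, dose-response model or covariate-adjusted outcome model is described. Propensity matching is described only for control versus intervention.

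**The concern.** The bands are 8 h wide, 36 h wide and open-ended. A patient first fed at 13 h and one fed at 47 h count as the same exposure, while 11 h and 13 h count as different. Variance analysis also ignores the order of the bands. Both features cost power if the outcome changes steadily with feeding time.

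These comparisons are the plan's only same-period evidence on feeding time, because the main comparison sets prospective patients against historical ones. Feeding time within the prospective group is not described as assigned at random, and the plan itself sets out to model what influences it. Sicker patients may be fed later, and none of the listed tests would separate that from an effect of feeding time.

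A smaller wording point: the first two bands both include exactly 12 h.

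**Working it through.** **Inputs.** From the documents: cut-points at 12 h and 48 h, a lower limit of 4 h, and significance at 0.05 (taken as two-sided). The documents give no sample size, effect size, standard deviation or feeding-time distribution, so there is no planned figure to reproduce. Everything else below is an assumption.

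**Step 1: exposure information kept by the bands.** The share kept is R = 1 − (within-band variance ÷ total variance). For feeding times uniform over 4-72 h:

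- within-band: (8/68)(8²/12) + (36/68)(36²/12) + (24/68)(24²/12) = 0.63 + 57.18 + 16.94 = 74.7
- total: 68²/12 = 385.3
- R = 1 − 74.7/385.3 = 0.806, so 19.4% is lost, about three quarters of it in the 12-48 h band (57.18/74.7).

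Other assumed distributions:

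| Feeding times | R |
|---|---|
| Uniform 4-96 h | 0.80 |
| Log-normal, median 12, 24, 36 h | 0.76, 0.75, 0.68 |
| Equal thirds, uniform within bands | 0.87-0.89 |
| 60/30/10 split | 0.87 |
| Tightly clustered within bands | 0.99 |

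The loss therefore runs from about 1% to 32%.

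**Step 2: large-sample power for a linear effect.** A one-degree-of-freedom test with 80% power has noncentrality (1.96 + 0.84)² ≈ 7.85. A three-group test has two degrees of freedom and noncentrality 7.85 × R. Its power is 53% at R = 0.68 and 71% at R = 0.99. Even with nothing lost (R = 1) it is 71%, so about 9 points are due to the unordered test alone. Regaining 80% needs 1.23/R times the patients, that is, 1.24 to 1.81 times.

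**Step 3: power at plausible sizes.** Take a correlation of 0.3 between feeding time and outcome (r² = 0.09). Noncentrality is n·r²/(1 − r²), or 60 × 0.09/0.91 = 5.93 and 90 × 0.09/0.91 = 8.90. For uniform times, banding lowers r² to 0.09 × 0.806 = 0.0725, giving 60 × 0.0725/0.9275 = 4.69 and 90 × 0.0725/0.9275 = 7.04. From the noncentral F distribution:

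| | n=60 | n=90 |
|---|---|---|
| Continuous, 1 df | 67% | 84% |
| 2 df, nothing lost | 56% | 75% |
| Three bands, 2 df | 46% | 64% |

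In this case roughly half the gap is degrees of freedom and half is banding.

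Simulation with times spread over 4-72 h or clustered in the bands, and a true effect linear in hours or in log hours, gives three-band variance analysis 43-51% against log-time regression 58-66% at n=60, and 64-74% against 78-85% at n=90. Repeat runs with other definitions of clustering moved these limits by a few points. A one-degree-of-freedom trend test on the same bands gives 52-62% at n=60.

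**Step 4: effects that are not smooth** (n=60, r = 0.3). For a step at 48 h, the bands have 53-54% power and log-time regression 27-44%. For a step at 24 h, inside the middle band, the order reverses: 24-36% against 49-55%.

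**The case against.** The bands have more behind them than slicing a continuous variable. Controls fast for at least 48 h on parenteral nutrition, so the after-48 h band mirrors the control regimen, and the 4 h limit is the enteral group's own fast. Comparing regimens is a legitimate question, and a single slope treats a change of feeding route as a smooth dose. This stands: only the 12 h cut has no visible basis.

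A reader might infer that banding discards most of the exposure information. The documents give no distribution that would show this, and under the assumed ones 68-99% of the variance is kept. A reader might also infer that continuous analysis is always better. That holds for smooth monotone effects; for a threshold at 48 h it is worse, and the documents do not say which shape is expected. Nor is the whole power gap due to banding: a trend test on the same bands recovers part of it, and nearly all of it when times are clustered.

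A three-knot spline used for inference also spends two degrees of freedom and gives back most of the gain (53-55% at n=60, against 42-51% for the bands in the same run). It is useful as a shape check only.

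Finally, more power does not cure confounding, which is the larger threat here. That also stands, and it is why the adjustment matters at least as much as the continuous term.

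**Conclusion.** The point holds in limited form. Feeding time is available as a number, but for albumin, inflammatory factor and defecation time it is used as an exposure only in three unordered bands, without adjustment, in a comparison not described as randomised or matched. For a smooth monotone effect the loss of power is material: with the ranges above, roughly 10 to 20 points at n=60 or 90, part of it from the unordered test. That size rests on the assumed sample sizes, r = 0.3 and the assumed feeding-time distributions.

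The documents do not support reading this as a flaw in the primary analysis. The rebleeding, mortality, hospital-stay and cost comparisons between the two groups do not use the bands. Nor do they support replacing the bands: which analysis is stronger depends on an effect shape that is not given. The 12 h overlap is a wording matter affecting only patients fed at exactly that hour, and adds nothing to the power argument. This is an optional improvement to supporting analyses.

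**What to change.** In Statistical analysis:

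- Keep the EEN/DEN/PN comparison.
- Add a pre-specified regression of albumin, inflammatory factor and defecation time on log hours to first feed, reporting the effect per doubling of time. At minimum, add a trend test across the bands.
- Adjust the regression and the band comparison for the baseline Child-Pugh and MELD scores already collected.
- Use a three-knot spline to check the shape, not as the main test.
- Define the first two bands so that exactly 12 h falls in only one of them for analysis.

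The cost is plan wording and one more analysis per outcome; no new data are needed. The downside is a shape assumption: if the true effect is a threshold at a cut-point, especially 48 h, the log-time term can do worse than the bands, which is why both should be reported.
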